#### 2.2.3 Study Populations, Subject Selection, Recruitment and Study Schedule

Sampling design - only patients that have been referred for a transthoracic echocardiogram will be included as part of this study. Patient referrals will be screened to assess whether the patients fit into either of the three study groups. On patient arrival, patients that are deemed to be eligible thus far will be provided with an explanation of the study, patient information documents, and written informed consent is to be invited and received. Departmental sonographers may initiate Research discussion with patient either pre-during or post-scan, prior to the CI explaining the study in full and obtaining written informed consent. Providing that the transthoracic scan images are of a good enough quality to obtain strain measurements, the patient will be included as part of the study. Recruitment options will be tailored to the participant and may be either remotely or at time of clinic visit. Once potential candidates have been screened, it is envisaged that the invitation letter, Participant Information Sheet (PIS), Informed Consent Form (ICF) and a template ICF will be posted to the participant along with their appointment letter for an echocardiogram. This will allow plenty of time for potential participants to read over the PIS. The patient then may be contacted prior to their appointment via telephone to discuss the study and participant involvement and give verbal consent. If this is not feasible, the study should be discussed with patient during their appointment visit and written consent can be obtained. If the CI is not able to discuss the study with the patient at either of these times, the patient may be telephoned following their scan to discuss and provide verbal consent.

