#### 2.2.2 Study Overview

- Study design quantitative, observational, case-control study.
- Patients will be assigned to one of three groups: control group (normal sinus rhythm), disease-control group (controlled hypertension) and disease group (chronic atrial fibrillation).
- Patients will be required to visit the department on one occasion. This will be as part of either a routine or urgent referral for a transthoracic echocardiogram (TTE).
- TTEs are stored on both the ultrasound machines and computer picture archiving systems (PACS). Measurements can be taken on either the ultrasound machine or on the PACS following the patient's scan. The data obtained from these scans that will be utilised include patient demographics, heart rate and rhythm, LA area and volume measurements as well as LA strain measurements. This will be pseudo-anonymised using two Excel spreadsheets and the document will be password encrypted on a NHS OneDrive account
- Study site: within the Cardio-Respiratory department at Withybush General Hospital, there are five sonographers. This creates a throughput of approximately 60 TTE scans per week. With an expected data collection period of five months, this would equate to approximately 1200 outpatient scans factoring in annual leave and sickness. Additionally, inpatient scans can boost this number, but is dependent on current demand.

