#### 2.2.5 Power Calculation

The study aims to investigate significant differences in atrial strain values between subjects with atrial fibrillation (AF), hypertension (no AF), and healthy volunteers. To

achieve statistical power for this study, a large enough sample size must be obtained. This will be achieved via the use of power calculations utilising G\*Power 3.1 Statistical support has been provided and a sample size calculation was based on data found within the literature and involved detecting the smaller difference of left atrium contractile % between subjects with atrial fibrillation and healthy volunteers. The following criteria will be utilised: alpha level of 0.05, beta level of 15% and statistical power of 85%. Hence using this minimum value to determine our sample size (expected difference of 4.0, power = 0.85 and SD  $\pm$  7.5) and one-way ANOVA at three levels, a minimum sample size of at least 78 subjects in each group will be required for this study, total of 234 participants required. See Appendix Figures 1 & 2 for power calculation plots.

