# 3.2 Informed Consent Procedures

The CI will be responsible for inviting and receiving informed consent. Once potential candidates have been screened, it is envisaged that the invitation letter, PIS, ICF and a template ICF will be posted to the participant along with their appointment letter for an echocardiogram. The study team will telephone participants after they have received this information and prior to their TTE to explain the study details and to confirm whether they are interested in participating. Verbal, telephone consent can be given and recorded at this time. Written consent can also be given if the patient wishes to complete the received ICF, following the template ICF. Additionally, written consent may be given if the research team are unable to contact the patient prior to their appointment. This can be completed during the echocardiogram appointment via written informed consent. If patients are not contactable prior to their appointment, or patients contacted during their appointment wish to have more time to think about their decision, the patient may be contacted following their scan to obtain verbal, telephone consent. Similarly, if the patient is not contactable prior to their scan, and the CI is unable to discuss the study with the patient during their appointment, then again, the patient may be contacted via telephone following the TTE to obtain verbal, telephone consent. Furthermore, if a potential candidate for the study is an in-patient, after the referral has been screened, the CI will go to the appropriate ward and provide the patient with the PIS, ICF and template ICF. The study may be explained to the patient at this time or at the time of the scan and only written informed consent can be given in this instance. Participants will be enrolled into the study once verbal or written consent have been given. If telephone consent is obtained, a copy of the signed consent form will be provided to the participant - either during their appointment visit or via post following the scan.

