## **3.3 Study Withdrawal**

Not all patients that provide written informed consent to be involved in this study will be deemed to be suitable and thus will not be included. If it is deemed that the quality of the TTE images obtained are not of a high enough quality (LA and LA walls must be fully visible and clear), then the subject will not be included in the study. This is because unclear images make it very difficult to accurately measure the LA area and volume. Clear LA wall borders are required to obtain atrial strain measurements. Including unclear images in the study will not provide an accurate measurement of LA strain for comparison. This will be explained to the patient prior to receiving consent and in the participant information sheet. The patient should be reassured that if their images are deemed to be of an inadequate standard for LA strain analysis, this does not mean that they do not have a diagnostic use as per referral request.

Participants have a right to withdraw their consent at any point in the study. As the data will have been pseudo-anonymised, if consent withdrawal is following data collection, the data obtained thus far must be uncovered to match the patient identifiers which are to be kept separately from patient data. Once the patient's data has been correctly identified, this will be removed from records and not included in any data analysis. However, if the participant chooses to withdraw following any processing of data, it may not be possible to remove this data from the analysis.

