# **Appendix**

[1] -- Friday, January 20, 2023 -- 20:14:29 F tests - ANOVA: Fixed effects, omnibus, one-way A priori: Compute required sample size Analysis: Input: Effect size f 0.2177324 =  $\alpha$  err prob = 0.05 Power  $(1-\beta \text{ err prob})$ 0.85 = Number of groups = 3 Output: Noncentrality parameter  $\lambda$ = 11.0933311 Critical F = 3.0349206 Numerator df = 2 Denominator df = 231 Total sample size = 234

Actual power

Figure 1: Computed sample size of 234 utilising G\*Power 3.1. The following criteria was used: effect size of 0.25, alpha level of 0.05, beta level of 0.15 (15%), statistical power of 0.85 (85%) and a total of 3 groups – control, disease-control, and control.

=

0.8509156

Figure 2: Plotted total sample size over power utilising G\*Power 3.1, producing a sample size of 234 to achieve 85% significance. The following criteria was used: effect size of 0.25, alpha level of 0.05, beta level of 0.15 (15%), statistical power of 0.85 (85%) and a total of 3 groups – control, disease-control, and control.

Research Project: Can left atrial strain measurements, and correlating changes in left atrium area and volume size, be used as an early predictor of atrial fibrillation? [name]

				2022 2023														2024					
TASK DESCRIPTION	PLAN START	PLAN END	0	N	D	J	F	М	A	М	J	J	A	s	0	N	D	J	F	м	A	М	
Phase 1: Project Planning																							
Task 1: Project Proposal	24/10/2022	16/12/2022																					
Task 2: R&D Protocol	01/11/2022	30/11/2022																					
Task 3: Sponsorship Review Group Preparation	09/11/2022	13/02/2023																					
Task 4: Health Research Authority / NHS Research Ethics Service Approval	13/02/2023	01/05/2023																					
Task 5: Literature Review	01/02/2023	21/04/2023																					
Phase 2: Data Collection & Analysis																							
Task 1: Identify, Screen & Recruit Patients	01/06/2023	01/11/2023																					
Task 2: Conduct Echocardiograms	01/06/2023	01/11/2023																					
Task 3: Calculate LA Area & Volume	01/06/2023	01/11/2023																					
Task 4: Calulate Strain Analysis	01/06/2023	01/11/2023																					
Task 5: Conduct Data / Statistical Analysis	01/11/2023	01/01/2024																					
Phase 3: Dissertation																							
Task 1: Refine Literature Review	01/12/2023	01/01/2024																					
Task 2: Refine Methodology	01/12/2023	01/01/2024																					

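### The study may first be raised, and consent taken, after the scan, with no requirement to approach all screened patients in order, so enrolment can depend on atrial findings already seen.

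*Combined protocol and SAP*

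**What the plan says.** Section 3.1 has the Chief Investigator screen inpatient and outpatient referrals. Sections 2.2.3 and 3.2 envisage posting the invitation and study documents with the appointment letter, followed by a telephone call before the scan. Section 2.2.3 also provides for explanation and written consent on arrival.

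Two provisions let the approach come later. In section 2.2.3, "Departmental sonographers may initiate Research discussion with patient either pre-during or post-scan", with the Chief Investigator then explaining the study and taking consent. In section 3.2, if the patient was not reached, wants more time, or the investigator was unavailable at the visit, "the patient may be contacted following their scan to obtain verbal, telephone consent". Section 3.2 makes consent the moment of enrolment. Inpatients are screened from the referral and may give written consent only.

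Section 2.2 states that LA area and volume are routine scan measurements. Section 4.10 places the extra (strain) measurements after the patient has left. Section 2.2.6 compares strain, area and volume between groups and records the expected direction: a difference between normal sinus rhythm (NSR) and atrial fibrillation (AF), and lower strain with a larger atrium.

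On numbers, section 2.2.5 gives "a minimum sample size of at least 78 subjects in each group will be required for this study, total of 234 participants required". For the five-month collection period, section 2.2.2 says "this would equate to approximately 1200 outpatient scans".

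**The concern.** In a case-control comparison, the way patients enter each group is part of the measurement. If the study is first raised during or after the scan, the person raising it may have seen the atrium. Two of the three compared measurements, area and volume, are then already available, and the third is expected to track them. Staff who expect small atria in NSR and large ones in AF could, without intent, pursue the patients who fit and let the others go.

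The later telephone call adds a further opening. Strain is measured after the patient leaves, and the consent call may fall in the same period. No section puts consent before strain, so the plan does not exclude a call made with the strain value known.

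Selection of this kind happens before any reading, so masked reading would not remove it. None of the analyses in section 2.2.6 would detect or correct it. Without a log of approaches, a reader of the results could not rule it out.

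**Working it through.** **1. The plan's own sample size.** Inputs from section 2.2.5: "alpha level of 0.05, beta level of 15% and statistical power of 85" per cent, and "expected difference of 4.0, power = 0.85 and SD" 7.5. The Appendix output gives "Effect size f 0.2177324".

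- f = (4.0/7.5) × √(1/6) = 0.21773, which corresponds to three equally spaced means with the outer two 4.0 apart.
- N = 234: λ = 234 × 0.21773² = 11.093, critical F(2, 231) = 3.0349, power = 0.8509.

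This matches the Appendix. The point here does not change the 234.

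**2. How much room there is to choose.** 234/1200 = 19.5%, but the 1200 are all outpatient scans before any eligibility filter, and inpatients are extra. The documents give no eligible share. Under assumed shares:

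| Eligible share of 1200 (assumed) | Eligible patients | Share of them needed (234/eligible) |
|---|---|---|
| 20% | 240 | 97.5% |
| 30% | 360 | 65% |
| 50% | 600 | 39% |
| 70% | 840 | 28% |

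Room for choice therefore runs from almost none to a great deal. It may also differ by group, since each group needs 78.

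**3. What choice could do.** Assumptions not in the documents:

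- no true NSR-AF difference;
- a fraction q of eligible patients enrolled in each group;
- a correlation r between the selection tendency and strain, acting in opposite directions in NSR and AF;
- SD 7.5, 78 per group, two-sided t-test at 0.05, and no adjustment of the SD for selection.

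Formulas:

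- Selection intensity: i = φ(z_q)/q. For q = 0.5, i = 0.3989/0.5 = 0.798.
- False difference: 2 × r × i × 7.5.
- Standard error: 7.5 × √(2/78) = 1.201.
- Type I error: rejection probability of the t-test with noncentrality (false difference)/1.201.

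| q | r | False difference (points) | Share of 4.0 | Type I error |
|---|---|---|---|---|
| 0.50 | 0.05 | 0.60 | 15% | 7.9% |
| 0.50 | 0.10 | 1.20 | 30% | 16.8% |
| 0.50 | 0.15 | 1.80 | 45% | 31.8% |
| 0.65 | 0.05 | 0.43 | 11% | 6.4% |
| 0.65 | 0.10 | 0.85 | 21% | 10.9% |
| 0.65 | 0.15 | 1.28 | 32% | 18.6% |
| 0.90 | 0.15 | 0.44 | 11% | 6.5% |

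If selection acts in one group only, the shift halves. At q = 0.5 and r = 0.15 it is 0.90 points, with type I error 11.5%.

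**4. What the text requires.** Sections 2.2.3, 3.1, 3.2 and 3.3 fix who screens, who consents and which images are unusable. None requires consecutive approach, approach of every screened patient, a rule for closing a group, a record of approaches and refusals, or consent before strain.

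**The case against.** The strongest reply is that the plan already has a pre-scan sequence: referral screening, posted invitation, telephone call, and explanation on arrival to patients judged eligible so far. Post-scan telephone consent is mainly a fallback for patients already screened, and the Chief Investigator takes consent whoever opens the discussion. This stands. A reader might infer that nothing governs who is approached; the documents do not support that. What is missing is narrower. The postal route is only envisaged, the list does not bind whom staff pursue, and the sonographer provision is not confined to it.

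A reader might also infer that the study picks one eligible patient in five. The documents do not support that either. The 1200 precede strict criteria: controls normotensive and otherwise healthy, no valve disease in either control group, EF of at least 50%, age 50 or over, usable images and tracking, plus age matching. And 78 per group is a minimum, not a cap.

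Finally, strain is not known at an in-visit approach under section 4.10, so selection then could act on strain only through visible LA size, appearance or image quality. The correlations and the opposite-direction assumption are not from the documents, and a null NSR-AF difference runs against the literature the protocol reports. This too stands, and it makes the error rates illustrations rather than estimates. It does not close the opening for area and volume, which are outcomes in their own right, nor for a telephone call made after strain is computed.

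**Conclusion.** The concern holds as a weakness in the recruitment rules. The text expressly permits first approach and enrolment after the scan, when two tested outcomes are visible, and it neither binds approach to the pre-scan list nor puts consent before strain. That shows selection is possible, not that it will happen.

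The size cannot be determined from the documents. If half of eligible patients are enrolled and selection correlates 0.05 to 0.15 with strain in opposite directions, the false NSR-AF difference is 0.6 to 1.8 points and type I error is 8% to 32%. If 90% or more are enrolled, type I error is at most about 6.5% over the same correlations. It would be wrong to report 8% to 32% as this study's error rate. The case for change rests on a plain gap in the text and a low cost of closing it, not on a demonstrated bias.

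**What to change.** In sections 2.2.3 and 3.2:

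1. Record the provisional study group and the decision to approach from the referral, before the scan.
2. Approach every listed patient in appointment order, within the age-matching constraint, until each group has 78 analysable patients. Counting analysable patients matters because section 3.3 says "Not all patients that provide written informed consent to be involved in this study will be deemed to be suitable" and no allowance is added to the 234.
3. Limit sonographer-initiated discussion and post-scan telephone consent to patients already on the list.
4. Do not compute strain until consent is recorded.
5. Some eligibility can be settled only on the scan. Apply those exclusions (EF, valve disease, image quality, tracking), and any change of group because of the rhythm found, by the stated criteria before strain values are seen.
6. Report numbers screened, approached, consenting and excluded, by group.

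The cost is a simple log kept by the investigator who already screens referrals. No scan or visit is added and the sample size stays at 234. Some ad hoc post-scan recruits are lost, so accrual may be slightly slower.

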#### 2.2.4 Eligibility Criteria

Patients must be in one of the following categories to be included: normal sinus rhythm, normal sinus rhythm with controlled hypertension and chronic atrial fibrillation (persistent or permanent). Patients with paroxysmal AF may also be included but only as part of subsequent analysis when comparing strain measurements between AF groups. Additionally, eligible patients must conform to the following inclusion and exclusion criteria.

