#### 2.2 Method

Patient selection:

Potential candidates for this study will have been referred for a TTE by a healthcare professional. The referrals will be reviewed and if the patient meets the initial eligibility criteria, they will be considered as part of this study. The initial eligibility criteria consist of being over the age of 50 (although patients will be age-matched across the three groups) and falling within the control (normal sinus rhythm), disease-control (controlled hypertension) or disease groups (chronic AF).

Data collection:

The images obtained from the TTE scan will be stored on the ultrasound machine as well as the picture archiving systems (PACS) on the computer. The measurements to be compared are:

- Left atrium area
- Left atrium volume
- Left atrium strain measurement and analysis using the R wave

The first two measurements are routinely performed during TTEs, but atrial strain measurements are not routinely performed. This additional measurement will not affect or delay the TTE results and report from being sent back to the referrer or delay any further correspondences with other healthcare professionals. Atrial strain measurements will be conducted using the AFI LA atrial strain tool provided by GE Healthcare. These three measurements will be compared across the three groups and tested for a statistically significant difference. Providing that there is a significant

difference, particularly between the control and disease groups, a subsequent comparison will be conducted between the three groups of AF using the existing data.

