#### Inclusion criteria:

- Criterion 1: subjects will be included in the study if they are within one of the following groups:
  - Known to be in normal sinus rhythm, are normotensive and have no underlying health problems.
  - Known to be in normal sinus rhythm and have controlled hypertension. This must have been diagnosed by a healthcare professional and the patient should be taking appropriate antihypertensive medication.
  - Known to have chronic atrial fibrillation (persistent or permanent AF). This must have been diagnosed by a healthcare professional and the patient should be appropriately anticoagulated.
- Criterion 2: subjects should ideally be ≥ 50 years, but subjects will be age matched across all three groups.
- Criterion 3: patients should have an EF  $\ge$  50%.
- Criterion 4: good quality TTE images.
- Criterion 5: No valvular pathologies.
  - Patients with AF that have < moderate valvular pathologies may be considered (as per the British Society of Echocardiography Guidelines).

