#### 2.2.6 Statistical Analysis Plan

Continuous data normality will be assessed utilising the Shapiro-Wilk test. Nonparametric data will be analysed via Mann-Whitney U tests and Kruskal-Wallis oneway ANOVA tests. If data shows a normal distribution, to compare the LA strain values between the control (NSR) and disease (AF) groups an independent T-test can be performed; this will establish whether there is an initial statistically significant difference between the two. Following this, to compare the mean strain values for each phase between the three groups, a one-way ANOVA must be performed. A one-way ANOVA can also be performed to determine any significant differences between the strain values between AF groups. These data analysis methods will also be repeated to analyse LA area and volume. To assess whether LA area and volume size correlate with LA strain, a Pearson correlation coefficient must also be performed. Furthermore, to determine whether LA strain may be used as an early predictor of AF, linear regression models must be adapted. For categorical data, such as gender, chisquared tests will be performed to determine any significant difference between groups. All statistical tests will be performed using the Prism GraphPad software.

It is expected that there will be a significant difference in strain values between NSR and AF participants. It is also expected that an increase in LA area and volume size will correlate with a decrease in LA strain values.

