# 3. Screening, Consent and Withdrawal

# 3.1 Screening Duties

The Chief Investigator will be responsible for screening potential participants. This will be done by reviewing both in-patient and out-patient referrals to look for patients that are in one of the following categories: normal sinus rhythm, normal sinus rhythm with controlled hypertension and chronic atrial fibrillation. Subsequently, this can be further refined by excluding patients based on age, valvular pathologies and ventricular dysfunction.

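### The secondary AF-subtype comparison ignores the recorded scan rhythm, so a paroxysmal versus persistent or permanent difference should not be read as atrial decline

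*Combined protocol and SAP*

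**What the plan says.** **Who enters.** Section 2.2.4 names three categories and then adds an exception: "Patients with paroxysmal AF may also be included but only as part of subsequent analysis when comparing strain measurements between AF groups". The next sentence reads: "Additionally, eligible patients must conform to the following inclusion and exclusion criteria". The AF entry of inclusion criterion 1 is "Known to have chronic atrial fibrillation (persistent or permanent AF", with no paroxysmal entry. Section 2.2.3 states: "Patient referrals will be screened to assess whether the patients fit into either of the three study groups". Section 3.1 lists the screening categories as "normal sinus rhythm, normal sinus rhythm with controlled hypertension and chronic atrial fibrillation".

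**What is analysed.** Under Section 2.2, if the main comparison is significant, "a subsequent comparison will be conducted between the three groups of AF using the existing data". Section 2.2.6 gives the method: "A one-way ANOVA can also be performed to determine any significant differences between the strain values between AF groups". Kruskal-Wallis is the non-parametric alternative. Neither test has a rhythm term, stratum or restriction.

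**What is recorded.** Section 2.2.2 provides for one visit, and the data taken from the scan include "patient demographics, heart rate and rhythm, LA area and volume measurements as well as LA strain measurements". Section 2.4 states that there is no follow-up.

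**What is expected and concluded.** Sections 1 and 1.1 expect no contractile strain in AF and warn that this phase may not be analysable. Section 1 regards conduit and reservoir strain as still comparable. Section 2.1 presents the subtype comparison as evidence on deterioration. Section 2.3 says differences may be observed that suggest decline as AF worsens and lasts longer.

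**The concern.** The comparison sorts patients by diagnosis, but strain is measured in whatever rhythm is present at one appointment. No section requires paroxysmal patients to be in a particular rhythm at that scan. If some are in sinus rhythm while the persistent and permanent patients are in AF, the subtype means can differ even when strain, within a given rhythm, is the same in all three subtypes.

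What is at stake is the conclusion. A single scan per patient can show only that groups of patients differ. It cannot show that strain falls as AF progresses, and without using rhythm it cannot separate AF type from rhythm at the scan. The data item needed to examine this is already being collected.

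A smaller matter of wording goes with it: the paroxysmal exception in Section 2.2.4 is not carried into inclusion criterion 1 or either screening section.

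**Working it through.** **1. The plan's own figure.** Inputs from Section 2.2.5: difference 4.0, SD 7.5, three groups, alpha 0.05, power 0.85. With the third mean midway, f = (4.0/7.5)/√6 = 0.2177. Then λ = f² × 234 = 11.093, critical F(2, 231) = 3.035 and power = 0.851. This reproduces the program output in the Appendix. All 234 are allotted as 78 to each of the three main groups, so the plan gives no number for paroxysmal patients and no size for the subtype comparison.

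**2. Illustration of the rhythm effect.** Inputs from the documents: 4.0 points, SD 7.5, alpha 0.05. Assumptions that the documents do not give:
- the 4.0 points are purely a rhythm effect;
- there are 39 patients per subtype;
- all persistent and permanent patients are in AF at the scan;
- a share p of paroxysmal patients is in sinus rhythm;
- subtype has no effect beyond rhythm.

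The paroxysmal mean is then shifted by D = 4.0p. The average within-group variance is σ² = 7.5² + 16p(1−p)/3, and λ = 39 × (2/3) × D²/σ². Critical F(2, 114) = 3.076.

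| p | D (points) | σ² | λ | Chance that the ANOVA is significant |
|---|---|---|---|---|
| 25% | 1.0 | 57.25 | 0.454 | 8% |
| 50% | 2.0 | 57.58 | 1.806 | 20% |
| 75% | 3.0 | 57.25 | 4.087 | 41% |

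Simulation with 100,000 studies per setting agrees (0.084, 0.203, 0.413; 0.049 at p = 0).

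**3. Sensitivity to the assumptions** (p = 25%, 50%, 75%):
- rhythm effect 2.0 points, 39 per subtype: 6%, 9%, 13%;
- rhythm effect 1.0 point, 39 per subtype: 5%, 6%, 7%;
- rhythm effect 4.0 points, 20 paroxysmal and 39 in each other subtype: 7%, 14%, 27%;
- rhythm effect 4.0 points, 78 per subtype: 12%, 37%, 72%.

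**4. What using rhythm does.** In the step 2 setting, limiting the ANOVA to patients in AF at the scan gives 5% at each p. In a separate simulation with 20 or 39 paroxysmal patients and a shift of 4 or 8 points, a rhythm covariate gives 4.7% to 5.7%.

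**5. Precision lost by restricting.** For paroxysmal versus 39 permanent patients, the 95% CI half-width is t(0.975, n+37) × 7.5 × √(1/n + 1/39). With n = 39, 29, 20 and 10 paroxysmal patients this is 3.4, 3.7, 4.1 and 5.3 points. The last three sizes are roughly 75%, 50% and 25% of 39.

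**The case against.** Several counter-arguments have force.

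- **Eligibility.** A reader might infer that no paroxysmal patient can be enrolled. That is a strained reading. Section 2.2.4 states the exception openly, the exclusion criteria do not bar paroxysmal AF, and the sentence requiring conformity can be taken to add the remaining criteria (age, EF, valves, image quality). Likewise, existing data in Section 2.2 can mean all scans already collected, paroxysmal ones included. What stands is an inconsistency between sections.
- **Type I error.** A reader might take the percentages above as an inflated false-positive rate. They are not. If more paroxysmal patients are in sinus rhythm, the group means truly differ and the ANOVA is right to detect it. The error would lie in the interpretation.
- **Relevance of the 4.0 points.** This is a contractile difference between AF patients and healthy volunteers, so it may include disease effects as well as rhythm. Section 1.1 doubts that the contractile phase can be analysed. The documents give no rhythm effect for reservoir or conduit strain, and a small effect would matter little. This stands: the mechanism is shown, its importance is not.
- **Rhythm as part of the disease.** Being in sinus rhythm some of the time is arguably part of what paroxysmal AF is, so removing rhythm answers a different question. That is a reason to report both analyses. It does not justify inferring decline.
- **Tentative wording.** Section 2.3 is cautious and the ANOVA is optional. The objectives in the Study Summary are firmer, so some softening is still due.

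**Conclusion.** The point holds as a minor, low-cost one. The subtype comparison is secondary and conditional, and as planned it cannot distinguish AF type from rhythm at the scan. A paroxysmal versus persistent or permanent difference may therefore be partly or wholly due to rhythm, and single scans do not support a statement about deterioration.

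How much this matters is unknown for reservoir and conduit strain. The range of 8% to 41% applies only under the stated assumptions for contractile strain, and drops to 5% to 7% if the rhythm effect is 1 point.

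A reader might infer that the main result is compromised as well. The documents do not support that: Section 2.2.4 keeps paroxysmal patients out of the three-group comparison, and the 234 reproduces.

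**What to change.** 1. **Section 2.2.6.** Tabulate scan rhythm by AF subtype. Beside the planned ANOVA, report as a sensitivity analysis the subtype comparison among patients in AF at the scan, or stratified by rhythm where both rhythms occur. Give pairwise differences with 95% CIs. Attribute a paroxysmal difference to AF subtype only if the restricted pairwise estimate is consistent with it, and say so if too few paroxysmal patients were in AF to tell.
2. **Sections 2.1 and 2.3** (and the matching text in the Study Summary and Section 1.1). Describe the result as an exploratory between-patient difference, not as deterioration or decline.
3. **Inclusion criterion 1, Sections 2.2.3 and 3.1.** Align these with the paroxysmal exception in Section 2.2.4, and state that paroxysmal patients are additional to the 234.

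A rule requiring significance in both the planned and the restricted ANOVA is not advised. For an assumed true gradient of 4/2/0 points (paroxysmal/persistent/permanent), 39 per subtype and no rhythm effect, it cuts power from 54% to 26% when 75% of paroxysmal patients are in sinus rhythm. A persistent-permanent difference alone can also satisfy it: about 58% to 64% of simulated studies with a 4-point difference there and no paroxysmal effect beyond rhythm.

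**Cost.** Some wording, one table and one extra analysis of data already recorded. The restricted paroxysmal subset is smaller, may represent a higher AF burden, and gives the wider intervals shown in step 5 of the working. The stated conclusion becomes weaker.
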